# 9.2. Study Populations

For purposes of analysis, the following populations are defined:

- Enrolled: All participants who sign the informed consent
- **Safety:** All participants randomly assigned to study intervention and who received at least 1 dose of belcesiran/placebo. Participants will be analyzed according to initial dose received.
- **Pharmacokinetic:** All participants randomly assigned to study intervention and who received at least 1 dose of belcesiran and have at least 1 postdose PK assessment
- **Pharmacodynamic**: All participants randomly assigned to study intervention and who received at least 1 dose of belcesiran/placebo and have at least 1 postdose PD assessment
- **Evaluable**: All participants randomly assigned to study intervention and who received at least 50% of planned doses of belcesiran/placebo

Additional subpopulations may be included for sensitivity analysis. These will be detailed in the SAP.

# 9.3. Statistical Analyses

#### 9.3.1. Analyses of Primary Endpoints

#### 9.3.1.1. Safety Analysis

All safety analyses will be performed on the Safety Population. Adverse events will be defined as TEAEs if they have a start date on or after the administration of study drug during the treatment period, or if they occur prior to the administration of study drug and worsen in severity/grade or relationship to the study intervention after the administration of study intervention during the treatment period. Frequency and percentages will be used to summarize TEAEs, SAEs, and AEs of special interest by relationship. Laboratory values will be reported by grade and summarized, if applicable.

Change from baseline and observed values will be summarized where applicable. Laboratory analytes will be presented by a shift from baseline and graphically represented in mean values over time where applicable. Vital signs, ECG, and PFTs (i.e., FEV1, FVC, FEV1/FVC, and DLCO) will be summarized as continuous parameters.

# 9.3.1.2. Analysis of Serum and Liver Z-AAT Concentrations

The primary endpoint for Cohort 3 of this study is the percentage change from baseline in serum and liver Z-AAT protein concentration at week 24.

The primary endpoint for Cohort 3 will be analyzed by using a linear log-normal regression model. Statistical testing for the primary endpoint of Cohort 3 will be carried out using the Hocheberg testing procedure for the following comparisons: (active high dose vs. placebo) and (active low dose vs. placebo). The linear log-normal regression model will include treatment, baseline value (log transformed) and randomization stratification factor of fibrosis types (F1, F2, F3, and F4) as covariates.

#### 9.3.2. Analyses of Secondary Endpoints

#### 9.3.2.1. Pharmacokinetic Analyses

Pharmacokinetic analyses will be performed on all participants who received at least 1 dose of belcesiran and have sufficient data for at least one evaluable postdose PK assessment. Actual sampling times will be used for all parameter estimations.

Plasma concentrations and PK parameters will be listed and summarized by group and by time point with descriptive statistics. The arithmetic mean, SD, CV%, geometric mean, geometric CV%, minimum, median, and maximum will be presented.

Additional PK parameters may be estimated if deemed appropriate. Details will be provided in the PK Analysis Plan. Analysis of PK parameters may be reported in a supplement to the CSR.

#### 9.3.2.2. Analyses of Fibrosis, Steatosis, and Inflammation

Changes from Baseline in liver histology including METAVIR and Ishak scores will be analyzed by descriptive statistical methods. METAVIR and Ishak scores will summarized and, if applicable, analyzed using modeling techniques, which will be described in the SAP.

#### 9.3.3. Exploratory Analyses

Exploratory analyses will be conducted as deemed appropriate and will be detailed in the SAP.

Descriptive summaries will be provided for the following exploratory endpoints: FibroScan® score, ELF score, and CK-8. Values, changes, and percent change for each parameter will be analyzed, when applicable.

Further supporting analyses such as correlation analyses between biomarkers and/or liver histology parameters might be performed to better understand the effect of belcesiran, if applicable.

#### 9.4. Interim Analyses

There are 3 interim analyses (IAs) planned for this study. The first interim analysis (IA1) will be conducted when all participants in Cohort 1 have completed 24 weeks of treatment. The second interim analysis (IA2) will be performed when all participants in Cohort 2 have completed 48 weeks of treatment. The third interim analysis (IA3) will be performed when all the participants in Cohort 3 have completed 24 weeks of treatment. As part of the IAs, all study site personnel will remain blinded, but the Sponsor will be unblinded. Details of unblinding including the list of unblinded Sponsor team members, will be described in the Study Specific Unblinding Plan. Additional interim analyses may be performed as needed.

The unblinded IA results will be reviewed and assessed by the DSMC while the participant, Investigator, and Outcome assessor will remain blinded. In addition, a small group of Sponsor personnel will be unblinded to participant level data as well to prepare and support regulatory interactions. Personnel who are unblinded to a critical fraction of the participant level data will subsequently not be allowed to participate in any aspects of the continued trial conduct.

Based on IA3 results, DSMC will make recommendation whether one dose is more favorable with respect to effect while showing no overall difference in safety. The Sponsor will make the final

decision whether to stop the least favorable dose-arm based on DSMC's recommendation and IA results.

Details of the analysis will be included in the SAP, which will be approved prior to the IAs.

#### 9.4.1. Data Safety Monitoring Committee

Table 77 shows the minimal required timing of reviews by the DSMC. Ongoing risk-benefit assessments will be conducted throughout the trial by the independent DSMC. In addition, DSMC will provide a comprehensive review of study safety, tolerability, and PK/PD data, along with a summary of cohort reviews across all cohorts and provide decisions. Further operational details will be prespecified in the DSMC charter.

Review of data from Study DCR-A1AT-101	The DSMC reviewed all available safety data from the first 3 cohorts of Study DCR-A1AT-101 and affirmed that it is safe to advance the dose level selected by M&S into a multiple dose regimen.
Review of sentinel pair dosing	The DSMC must review the available safety data collected on a sentinel pair of participants, through at least 3 weeks postdose before the remaining participants can be randomized and dosed. The data to be reviewed will be specified in the DSMC charter.
Review of first 10 participants randomized and dosed	The DSMC will review the available safety data collected on the first 10 participants to receive study intervention, through Day 29. The data to be reviewed will be specified in the DSMC charter.
After completion of Cohort 1 (IA1)	The DSMC will review the safety and efficacy data collected through the EOT (Week 24) visit for all participants in Cohort 1.
Occurrence of a potential stopping rule	The DSMC will review and adjudicate all AEs that constitute potential stopping rules, in addition to the cumulative safety data collected on all participants previously dosed. The DSMC will determine whether dosing and enrollment may resume as detailed in Section 7.1.
After completion of Cohort 2 (IA2)	The DSMC will review the safety and efficacy data collected through the EOT (Week 48) visit for all participants in Cohort 2.
Interim Analysis 3 (IA3)	The DSMC will review the safety and efficacy data collected through the Week 24 visit for all participants in Cohort 3.
Additional IA if performed	The DSMC will review the safety and efficacy data collected through additional IA if performed.

 Table 77:
 Minimum Timing of the Data Safety Monitoring Committee Data Reviews

Abbreviations: AE: adverse event; DSMC: Data Safety Monitoring Committee; EOT: end of treatment; IA: interim analysis; M&S: modeling and simulation.

# 10. SUPPORTING DOCUMENTATION AND OPERATIONAL CONSIDERATIONS

# 10.1. Regulatory, Ethical, and Study Oversight Considerations

#### 10.1.1. Regulatory and Ethical Considerations

This study will be conducted in accordance with the protocol and with the following:

- Consensus ethical principles derived from international guidelines including the Declaration of Helsinki and CIOMS International Ethical Guidelines
- Applicable ICH GCP Guidelines
- Applicable laws and regulations

The protocol, protocol amendments, ICF, IB, and other relevant documents (e.g., advertisements) must be submitted to an IRB/IEC by the Investigator and reviewed and approved by the IRB/IEC before the study is initiated.

Any amendments to the protocol will require IRB/IEC approval before implementation of changes made to the study design, except for changes necessary to eliminate an immediate hazard to study participants.

The Investigator will be responsible for the following:

- Providing written summaries of the status of the study to the IRB/IEC annually or more frequently in accordance with the requirements, policies, and procedures established by the IRB/IEC
- Notifying the IRB/IEC of SAEs or other significant safety findings as required by IRB/IEC procedures
- Providing oversight of the conduct of the study at the site and adherence to requirements of 21 CFR, ICH guidelines, the IRB/IEC, European regulation 536/2014 for clinical studies (if applicable), and all other applicable local regulations

#### **10.1.2.** Financial Disclosure

Investigators and sub-investigators will provide the Sponsor with sufficient, accurate financial information as requested to allow the Sponsor to submit a complete and accurate financial certification or disclosure statements to the appropriate regulatory authorities. Investigators are responsible for providing information on financial interests during the study and for 1 year after completion of the study.

#### 10.1.3. Informed Consent Process

The Investigator or his/her representative will explain the nature of the study to the participant and answer all questions regarding the study.

Participants must be informed that their participation is voluntary. Participants will be required to sign a statement of informed consent that meets the requirements of 21 CFR 50, local regulations, ICH guidelines, and the IRB/IEC or study center.

The source document must include a statement that written informed consent was obtained before the participant was enrolled in the study, and the date the written consent was obtained. The authorized person obtaining the informed consent must also sign the ICF.

Participants must be re-consented to the most current version of the ICF(s) during their participation in the study.

A copy of the ICF(s) must be provided to the participant.

A participant who is rescreened is required to sign another ICF.

#### **10.1.4.** Data Protection

Participants will be assigned a unique identifier by the Sponsor. Any participant records or datasets that are transferred to the Sponsor or Sponsor's designee will contain the identifier only; participant names or any information which would make the participant identifiable will not be transferred.

The participant must be informed that his/her personal study-related data will be used by the Sponsor in accordance with local data protection law. The level of disclosure must also be explained to the participant.

The participant must be informed that his/her medical records may be examined by Clinical Quality Assurance auditors or other authorized personnel appointed by the Sponsor, by appropriate IRB/IEC members, and by inspectors from regulatory authorities.

#### **10.1.5.** Committee Structure

The external DSMC will be comprised of an independent hepatologist and an independent pulmonologist, both of whom have experience in caring for patients with AATD, and a biostatistician who is also not involved in the study. The DSMC will provide a comprehensive review of study safety and tolerability data, along with a summary of cohort reviews and decisions. Further operational details will be prespecified in the DSMC charter.

The internal Novo Nordisk safety committee will perform ongoing safety surveillance. If new safety signals are identified, these will be evaluated by an internal safety committee. The safety committee may recommend unblinding of any data for further analysis, and in this case an internal trial independent ad hoc group will be established in order to maintain the blinding of the trial personnel.

#### 10.1.6. Dissemination of Clinical Study Data

After de-identification, individual data collected during the trial may be shared with investigators whose proposed use of the data has been approved by the sponsor.

All trial results will be posted to www.clinicaltrials.gov and www.clinicaltrialsregister.eu within 1 year of study completion.

#### 10.1.7. Data Quality Assurance

All participant data relating to the study will be recorded on electronic CRF unless transmitted to the Sponsor or designee electronically (e.g., laboratory data). The Investigator is responsible for verifying that data entries are accurate and correct by electronically signing the CRF.

The Investigator must maintain accurate documentation (source data) that supports the information entered in the eCRF.

The Investigator must permit study-related monitoring, audits, IRB/IEC review, and regulatory agency inspections and provide access to source data documents.

Monitoring details describing methods, responsibilities, and requirements, including handling of non-compliance issues and monitoring techniques (central, remote, or on-site monitoring) are provided in the Monitoring Plan.

Study monitors will perform ongoing source data verification to confirm that data entered into the eCRF by authorized site personnel are accurate, complete, and verifiable from source documents; that the safety and rights of participants are being protected; and that the study is being conducted in accordance with the currently approved protocol and any other study agreements, ICH GCP, and all applicable regulatory requirements.

The Sponsor or designee is responsible for the data management of this study, including the quality checking of the data.

The Sponsor assumes accountability for actions delegated to other individuals (i.e., Contract Research Organizations).

Records and documents, including signed ICFs, pertaining to the conduct of this study must be retained by the Investigator for at least 15 years after study completion unless local regulations or institutional policies require a longer retention period. No records may be destroyed during the retention period without the written approval of the Sponsor. No records may be transferred to another location or party without written notification to the Sponsor.

#### 10.1.8. Source Documents

Source documents provide evidence for the existence of the participant and substantiate the integrity of the data collected. Source documents are filed at the Investigator's site.

Data entered in the eCRF must be consistent with the source documents, or the discrepancies must be explained. The Investigator may need to request previous medical records or transfer records. Current medical records must be available.

#### 10.1.9. Study and Site Closure

The Sponsor designee reserves the right to close the study site or terminate the study at any time for any reason at the sole discretion of the Sponsor. Please see Section 7.1 for study stopping rules relating to participant safety. Study sites will be closed upon study completion. A study site is considered closed when all required documents and study supplies have been collected, and a study-site closure visit has been performed.

The Investigator may initiate study-site closure at any time, provided there is reasonable cause, and sufficient notice is given in advance of the intended termination.

Reasons for the early closure of a study site by the Sponsor or Investigator may include but are not limited to:

- 1. Failure of the Investigator to comply with the protocol, the requirements of the IRB/IEC or local health authorities, the Sponsor's procedures, or GCP guidelines
- 2. Inadequate recruitment of participants by the Investigator
- 3. Discontinuation of further study intervention development

# **10.1.10. Publication Policy**

The results of this study may be published or presented at scientific meetings. If this is foreseen, the Investigator agrees to submit all manuscripts or abstracts to the Sponsor before submission. This allows the Sponsor to protect proprietary information and to provide comments.

The Sponsor will comply with the requirements for publication of study results. In accordance with standard editorial and ethical practice, the Sponsor will generally support the publication of multi-center studies only in their entirety and not as individual site data. In this case, a coordinating Investigator will be designated by mutual agreement.

Authorship will be determined by mutual agreement and in line with the International Committee of Medical Journal Editors' authorship requirements.

# **10.2.** Clinical Laboratory Tests

The tests detailed in Table 88 will be performed by the central laboratory, with the exception of pregnancy testing and cotinine testing which will be performed locally. Laboratory testing required for immediate safety concerns may also be performed locally at the discretion of the Investigator.

Protocol-specific requirements for inclusion or exclusion of participants are detailed in Section 5 of the protocol.

Additional tests that are required for clinical management of the participant may be performed at any time during the study as determined necessary by the Investigator or required by local regulations.

Investigators must document their review of each laboratory report.

Laboratory Assessments	Parameters	
Hematology	Red blood cell count	White blood cell count:
	hemoglobin	lymphocytes, abs and %
	hematocrit	monocytes, abs and %
	platelet count	eosinophils, abs and %
	reticulocytes	basophils, abs and %
	mean corpuscular volume (MCV)	neutrophils, abs and %
	mean corpuscular hemoglobin (MCH)	
	mean corpuscular hemoglobin concentration (MCHC)	

 Table 88:
 Protocol-Required Laboratory Assessments

Laboratory Assessments	Parameters	
Clinical Chemistry	alanine aminotransferase (ALT) aspartate aminotransferase (AST) glutamate dehydrogenase (GLDH) gamma glutamyl transferase (GGT) alkaline phosphatase (ALP) bilirubin; total and direct lactate dehydrogenase (LDH) total cholesterol triglycerides	total protein albumin creatine kinase (CK) sodium chloride potassium creatinine urea (BUN) glucose
Routine Urinalysis	Specific gravity, pH, glucose, protein, blood, k leukocyte esterase by dipstick Urine protein-to-creatinine ratio (UPCR) Urine albumin-to-creatinine ratio (UACR) Microscopic examination (if blood or protein i	setones, bilirubin, urobilinogen, nitrite,
Other safety tests	
 
Total complement hemolytic activity (CH50): C3a, C5a, and Bb
 
Serum alpha fetoprotein (AFP)
 
Coagulation parameters: aPTT, PT, INR
 
Antidrug antibodies
 
C-reactive protein
 
Urine pregnancy test
 
	
Pregnancy testing	Serum or urine human chorionic gonadotropin (hCG) pregnancy test (as needed) (see Schedule of Activities in Section 1.3	
Other Screening Tests	
 
FSH (as needed in postmenopausal women only)
 
Urine drug screen (to include, at a minimum: amphetamines, barbiturates, cocaine, opiates, and benzodiazepines)
 
Serology (HIV antibody, HBsAg, and HCV antibody)
 
Antimitochondrial antibodies (if suspected for PBC)
 
HbA1c
 
Urine cotinine
 
	
Other Tests	
 
α-2 macroglobulin, haptoglobin, and apolipoprotein A1 (components of non-invasive fibrosis index)
 
Biomarkers of liver fibrosis (ELF, Pro-C3, tenascin)
 
Biomarkers of inflammation and liver apoptosis (CK-18, M30, and M65)
 
Samples for future analyses
 
Serum AAT (total and Z-AAT)
 
Liver Z-AAT, PAS-positive AAT globules
 
Liver histology, including fibrosis
 
	

Abbreviations: aPTT: activated partial thromboplastin time; EGF: epidermal growth factor; FSH: follicle-stimulating hormone; HbA1c: hemoglobin A1c; HBsAg: hepatitis surface antigen; HCV: hepatitis C virus; HIV: human immunodeficiency virus; IFN: interferon; IL: interleukin; INR: international normalized ratio; PBC: primary biliary cholangitis; PT: prothrombin time; SARS-CoV-2: severe acute respiratory syndrome coronavirus 2; TNF-α: tumor necrosis factor-alpha.

#### **10.2.1.** Samples for Future Analysis

The trial will involve collection of samples to be stored in a central archive for future use. Participants who do not wish to contribute samples for storage may still participate in the trial.

Participants must consent before samples are collected to be stored for future analysis.

The material to be collected is blood (whole blood, plasma and serum) and liver tissue. Blood samples will be collected as indicated in the SoA (Section 1.3).

Liver tissue will be collected from the liver biopsy at week 24, 48 and 96 as applicable.

Samples will be used to improve knowledge and understanding of the biology of the trial disease and related diseases, such as mechanism of action or treatment effect. The biosamples may be transferred to other countries and third parties including commercial vendors such as diagnostics developers for analysis. In case the participant withdraws his/her informed consent for biosamples for future analysis, the monitor must contact the Sponsor trial manager as soon as possible in order to have the samples withdrawn from storage. If the collected biosamples (serum, plasma, liver biopsy samples) will be used in the future, the participant and investigator will not become directly informed by Sponsor about the results.

# 10.3. Adverse Events: Definitions and Procedures for Recording, Evaluating, Follow up, and Reporting

#### **10.3.1. Definition of AE**

#### **AE/TEAE Definition**

An AE/TEAE is any untoward medical occurrence in a patient or clinical study participant, temporally associated with the use of study intervention, whether or not considered related to the study intervention. Therefore, an AE/TEAE can be any unfavorable and unintended sign (including an abnormal laboratory finding), symptom, or disease (new or exacerbated) temporally associated with the use of study intervention.

#### Events Meeting the AE/TEAE Definition

- Any abnormal laboratory test results or other safety assessments (e.g., ECG, radiological scans, vital signs measurements), including those that worsen from baseline, considered clinically significant in the medical and scientific judgment of the Investigator (i.e., not related to the progression of underlying disease).
- Exacerbation of a chronic or intermittent pre-existing condition including either an increase in frequency and/or intensity of the condition.
- New conditions detected or diagnosed after study intervention administration, even though it may have been present before the start of the study.
- Signs, symptoms, or the clinical sequelae of a suspected drug-drug interaction.
- Signs, symptoms, or the clinical sequelae of a suspected overdose of either study intervention or concomitant medication. Overdose per se will not be reported as an

AE/SAE unless it is an intentional overdose taken with possible suicidal/self-harming intent. Such overdoses should be reported regardless of sequelae.

#### **10.3.2. Definition of SAE**

If an event is not an AE per the definition above, it cannot be an SAE even if serious conditions are met (e.g., hospitalization for signs/symptoms of the disease under study, death due to progression of the disease).

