### 2.3.1.2. Risks Related to AAT Knockdown

There is currently little experience with AAT knockdown in patients with PiZZ AATLD. However, the knockdown of AAT could potentially worsen the related loss-of-function effects in the lungs, since it has been shown that subjects with Null mutations of the *SERPINA1* gene and thereby no Z-AAT production, are at a particularly high risk of emphysema. It is however important to note that the pulmonary manifestations in the Null mutation population usually develop after decades of total absence of the AAT protein (Fregonese et al, 2008).

In the DCR-A1AT-101 study, a mean knockdown of 78% was achieved and no clinically significant changes in lung function were noted on spirometry or DLCO, no dose-dependent changes were noted in repeat measurements of any spirometry parameter, and all Percent Predicted DLCO measurements remained within normal limits across all cohorts.

In addition, others have reported that no clinically meaningful changes in spirometry were observed after 40 weeks (N=16) or 72 weeks (N=4) of Z-AAT knockdown in patients with AATLD (Strnad et al., 2021).

To mitigate this risk, serial measurements of PFTs will be conducted throughout the study, and whenever applicable augmentation therapy will be able to restore absent serum AAT protein concentrations and anti-neutrophil elastase capacity to levels at the lower limit of normal (Wewers, 1987; Sandhaus et al., 2016; Chapman et al., 2015; Sorrells et al., 2015).

In study participants already on augmentation therapy at the initiation of the study, the risk of worsening the loss-of-function disease mechanism in the lungs is reduced because these study participants have non-mutated M-AAT levels restored to the lower limit of normal and this would not be affected by the Z-AAT knockdown (Chapman KR, Chorostowska-Wynimko J, Koczulla AR, Ferrarotti I, McElvany NG. Alpha 1 antitrypsin to treat lung disease in alpha 1 antitrypsin deficiency recent developments and clinical implications. Int J Chron Obstruct Pulmon Dis. 2018;13:419-432.

).

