### 2.3.4. Overall Benefit: Risk Conclusion

At present, no pharmacological therapies are approved for the treatment of patients with AATLD. These patients are at increased risk of developing cirrhosis and portal hypertension (PHT). Complications associated with PHT include gastrointestinal bleeding, ascites, encephalopathy, and reduced levels of platelets, or decreased white blood cell count. The standard-of-care includes the use of vasoactive drugs, endoscopic band ligation, and antibiotic prophylaxis. Patients failing standard-of-care treatment may undergo transjugular intra hepatic portosystemic shunt (TIPS) placement. Ultimately, the only cure for AATLD is liver transplantation.

Belcesiran has been shown to decrease serum AAT protein concentrations in healthy volunteers. In Study DCR-A1AT-101, the mean reduction in serum AAT concentration at EOT visit ranged from approximately 48% for the 1.0 mg/kg cohort to 78% for the 12.0 mg/kg cohort. Belcesiran treatment has the potential benefit to reduce the production and, hence, the accumulation of the misfolded Z-AAT protein in the liver. By eliminating the toxic protein, belcesiran may prevent liver disease progression, which ultimately may eliminate the need for liver transplantation.

Participants with AATLD could potentially benefit from the investigational drug. This potential benefit has not been proven and may be limited in duration to the treatment period of this trial.

The key potential risks associated with belcesiran include exacerbation of emphysema, a decline in lung function, elevations of LFTs, and injection site reactions. All these risks are monitorable and should be reversible over time after drug discontinuation or could potentially be treated with intravenous augmentation therapy in the case of knockdown-mediated lung function decline. In DCR-A1AT-101, single doses of belcesiran in healthy volunteers (up to and including 12 mg/kg) appeared to be safe and well tolerated. Repeat measurements of spirometry and DLCO indicated that normal lung function was preserved. No clinically significant or apparent dose-dependent increases in AST or ALT levels were observed.

In study participants already on augmentation therapy at the initiation of the study, the risk of lung function decline due to reduction of Z-AAT serum levels would be reduced because these study participants have non-mutated M-AAT levels restored to the lower limit of normal.

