### 8.3.1. Time Period and Frequency for Event Assessment

All AEs/SAEs will be collected from the signing of the ICF until the last day of study participation, including F/U.

Any medical condition that is present at the time that the participant is screened will be considered as baseline medical history and not reported as an AE. However, if the study participant's condition deteriorates after having received the first dose of Investigational Product during the study, it will be recorded as a TEAE.

Investigators are not obligated to actively seek AE or SAE after the conclusion of the study participation. However, if the Investigator learns of any SAE, including death, at any time after a participant has been discharged from the study, and he/she considers the event to be reasonably related to the study intervention or study participation, the Investigator must notify the Sponsor promptly.

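### Protocol Sections 10.3.1 and 10.3.2 let worsening be set aside as disease progression, against the protocol's own recording rule, so TEAE and SAE counts can miss the named lung and liver harms or split them between sites

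*Protocol*

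**What the plan says.** Two places in the protocol point away from recording.

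- Section 10.3.1, first bullet under the events that meet the definition: abnormal laboratory and other safety results count as AEs when "considered clinically significant in the medical and scientific judgment of the Investigator (i.e., not related to the progression of underlying disease").
- Section 10.3.2: an event that is not an AE "cannot be an SAE even if serious conditions are met (e.g., hospitalization for signs/symptoms of the disease under study, death due to progression", where the last example is a death that the illness itself causes.

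Three places point towards recording.

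- Section 10.3.1, general definition: an AE can be any unfavorable sign, "symptom, or disease (new or exacerbated) temporally associated with the use of study intervention", regardless of relationship to treatment.
- Section 10.3.1, second bullet: "Exacerbation of a chronic or intermittent pre-existing condition including either an increase in frequency and/or intensity of the condition" is an AE.
- Section 8.3.1: if a participant's baseline "condition deteriorates after having received the first dose of Investigational Product during the study, it will be recorded as a TEAE". No exception is made for progression.

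On the harms themselves, Section 2.3.4 states: "The key potential risks associated with belcesiran include exacerbation of emphysema, a decline in lung function, elevations of LFTs, and injection site reactions". Section 2.3.1.2 says that "the knockdown of AAT could potentially worsen the related loss-of-function effects in the lungs".

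The primary safety endpoint for Cohorts 1 and 2 (protocol Section 3, SAP Section 2.3.1) joins TEAEs with change from baseline in PFTs, ECGs, physical examination, vital signs and laboratory tests. Section 8.3.4 requires SAEs to reach the sponsor within 24 hours. Injection site reactions are the only AESI (protocol Section 10.3.3, SAP Section 3.7.1).

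**The concern.** Three of the four named key risks are worsening of organs that AATD already damages. In a PiZZ participant, a fall in FEV1, a transaminase rise or a liver-related admission caused by the drug could look like natural history, and a blinded investigator has little to tell them apart. The carve-outs ask the investigator to make that attribution before the event is counted, whereas a placebo-controlled safety comparison normally counts the event first and lets the arms be compared.

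At stake are the TEAE component of the primary safety endpoint, the counts of SAEs and of AEs leading to death in the SAP overview (Section 3.7.1), and expedited reporting. An admission or death classed as progression would appear in none of them. Because the protocol also contains the opposite instruction, the practical result is inconsistent classification between sites, of unknown direction and amount.

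**Working it through.** The protocol states no figure on this point, so the check is mainly a comparison of texts.

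**1. What each rule does with the same event**

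| Event after first dose | Rule that lets it drop out | Rule that records it |
|---|---|---|
| Liver test rise read as progression | 10.3.1, first bullet | 8.3.1; 8.2.7 (clinically relevant laboratory changes go in the AE section of the eCRF) |
| FEV1 or DLCO fall read as progression | 10.3.1, first bullet (PFTs sit under safety and other assessments, Section 8.2.5) | 8.3.1; 10.3.1 second bullet, if seen as exacerbation |
| Admission for worsening liver disease | 10.3.2 examples | 8.3.1; 10.3.1 general definition and second bullet |
| Death from liver disease progression | 10.3.2 examples | 10.3.1 general definition; 10.3.2 criterion 1 |
| Admission for emphysema exacerbation | 10.3.2, only if the disease under study includes the lung | 8.3.1; 10.3.1 second bullet |

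Every row has an entry in both columns. Section 10.3.2 is conditional on the event not being an AE, but that does not resolve the conflict. Its examples tell the reader that disease-related admissions and deaths do fall outside the AE definition, which the general definition does not say. The hospitalization criterion in the same section exempts elective treatment of a pre-existing condition only where it has not worsened, which again implies that worsening counts.

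**2. Which outputs depend on the classification**

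- Dependent: TEAE incidence, SAEs and AEs leading to death (SAP Section 3.7.1), and 24-hour reporting (protocol Section 8.3.4).
- Not dependent: by-visit FEV1, FVC, FEV1/FVC and DLCO (SAP Section 3.7.2) and laboratory values (SAP Section 3.7.3).
- Collected separately but with no planned table: number and severity of pulmonary exacerbations (protocol Section 8.2.6). The SAP specifies no summary of them; at most they appear in the listings of all data promised in SAP Section 7.

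**3. Weight of one event**

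Inputs: up to 8 + 8 = 16 participants in Cohorts 1 and 2, randomized 3:1 (protocol Section 9.1).

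- Belcesiran: 16 × 3/4 = 12, so one event is 1/12 = 8.3 percentage points.
- Placebo: 16 × 1/4 = 4, so one event is 1/4 = 25 percentage points.

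**4. Illustration of under-recording**

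Both the true event rate p and the share f withheld as progression are assumptions; neither is in the documents. With independent participants, the chance of at least one recorded event among 12 is 1 − (1 − p(1 − f))^12.

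| p | f = 0 | f = 25% | f = 50% |
|---|---|---|---|
| 5% | 46% | 37% | 26% |
| 10% | 72% | 61% | 46% |
| 20% | 93% | 86% | 72% |

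For example, p = 10% and f = 50% gives 1 − 0.95^12 = 46%, against 1 − 0.90^12 = 72% with full recording.

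**The case against.** The strongest reply is that the recording rule is already there. A site that follows Section 8.3.1 records the deterioration as a TEAE, and the TEAE definitions in protocol Section 9.3.1.1 and SAP Section 3.7.1 contain no progression exclusion. This stands to the extent that a reader who infers that the protocol simply excludes worsening of the underlying disease goes too far. The documents support a contradiction, not a uniform exclusion.

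Three other stronger readings also fail.

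- A reader might infer that the harms can vanish from the primary safety endpoint as a whole. They cannot: lung function and liver chemistry are scheduled components, summarized whatever their AE status.
- A reader might infer that the sponsor expects knockdown to harm the lungs. Section 2.3.1.2 presents a possibility, and adds that lung disease in people with Null mutations usually takes decades.
- A reader might infer that Section 10.3.2 plainly covers emphysema. The title names AAT-associated liver disease, so the disease under study may mean the liver only. The wider wording, "i.e., not related to the progression of underlying disease", is in 10.3.1 and is attached to laboratory and other safety results, not to every clinical event.

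There are also safeguards outside AE reporting, but they are partial. The FEV1 and DLCO criteria that go to the DSMC (Section 7.1.1.1) apply to participants not on augmentation therapy and need at least 2 tests over at least 3 months. Central liver alerts (Section 7.1.1.2) are independent of AE status. However, for participants with normal baseline liver tests, that section also asks for an attribution judgment before an elevation leads to discontinuation. Table 7 has the DSMC adjudicate AEs that may meet a stopping rule, so AE status gates part of the oversight. By-visit means of PFTs and laboratory values do not show admissions, decompensations or deaths.

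Finally, the trial stopped early and the SAP tests no hypotheses (SAP Sections 1 and 3.1.5). That lowers the inferential stakes, but descriptive counts of serious events are then the main safety result, and they are what is exposed.

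**Conclusion.** The point holds as an internal contradiction with a safety consequence. The first bullet of Section 10.3.1 and the examples in Section 10.3.2 allow abnormal safety results, disease-related admissions and deaths to be classed as neither AE nor SAE. Section 8.3.1, the general AE definition and the second bullet of 10.3.1 require deterioration to be recorded. Until these are reconciled, TEAE incidence, the SAE and death counts and 24-hour reporting can under-count the named harms or count them differently between sites. Serious liver events are directly within reach of the carve-out; for lung events the reach of 10.3.2 is ambiguous. The change-from-baseline parts of the primary safety endpoint are unaffected.

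The size cannot be estimated from the documents. The 8.3-point and 25-point figures show only the weight of one event at full enrollment, and would be larger with fewer participants. They say nothing about how often an event would be withheld. The table of recording probabilities rests wholly on assumed rates and shares. The conclusion itself depends on the wording alone.

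**What to change.** 1. In Section 10.3.1, delete the parenthetical "i.e., not related to the progression of underlying disease". In Section 10.3.2, delete the parenthetical giving disease-related hospitalization and death from progression as examples.
2. Add one sentence consistent with Section 8.3.1: worsening of lung or liver disease after the first dose is recorded as an AE, and as an SAE if a seriousness criterion is met, whatever its attribution to progression.
3. In the SAP, add a by-treatment summary of the number and severity of pulmonary exacerbations already collected under protocol Section 8.2.6.
4. Since dosing in Cohorts 1 and 2 has largely preceded any rewording, query before database lock any hospitalization or death that has no AE record, and classify it under the reconciled rule.

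The cost is two deletions, one added sentence, one extra table and a data query. The downside is a few more AE and SAE reports, some of them natural history, which the placebo arm helps to put in context, though with at most 4 placebo participants that context is thin.
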